6. HYPOTHESIS

Assumption 1: **Weight Loss** .

H1: The use of the "Zélé method" (**Tx1**) allows a greater weight loss (*pp*) than a hypocaloric diet (**Tx2**) in the same time (*t*).

Assumption 2.

H2: Tx1 is safe and with low or no adverse effects.

Assumption 3. **Metabolic conditions**

H3: *pp* with Tx1 allows the regulation of metabolic syndrome and its components.

H4: The state of controlled ketosis that occurs with Tx1 does not change pH or raise blood lactate levels.

Assumption 4 . **Body Composition**.

H5. Tx1 will produce a selective loss of fat and preservation of muscle mass.

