BMI	Indicator of body density determined by the ratio of body weight to body height.	BMI falls into these categories: below 18.5 (underweight); 18.5-24.9 (normal); 25.0-29.9 (overweight); 30.0 and above (obese).	Quantitative, Ratio, $BMI = \frac{\text{weight (kg)}}{\text{height squared (m}^2\text{)}}.$ Unit Kg/m ² , Minimum 11, Maximum 75	Data registration form,
Muscle Mass	Volume of total body tissue corresponding to muscle. ,	From the point of view of body composition, it corresponds to lean mass.	Quantitative, Ratio. Unit Kg. Minimum 10 Maximum 150	Data registration form Multi-frequency Bioelectrical Impedance Equipment
Fat Mass	Percentage of body weight made up of adipose tissue	Amount of fat in the body	Quantitative, proportion, Unit Percentage. Minimum 9 Maximum 80	Data registration form Multi-frequency Bioelectrical Impedance Equipment
Visceral Fat	Fatty tissue within the abdominal cavity, which includes visceral fat and retroperitoneal fat.	It is the most metabolically active fat in the body. Its increase is associated with metabolic complications of obesity.	Quantitative, Ratio. Unit Index. From 1 to 40	Data registration form Multi-frequency Bioelectrical Impedance Equipment
Bone Mass	Measurement of the amount of minerals (usually calcium and phosphorus) contained in the bones.	Skeletal weight	Quantitative, Ratio Unit Kg. From 1 to 7 kg.	Data registration form Multi-frequency Bioelectrical Impedance Equipment
Total body water	Amount of liquids, mainly water, found inside the body.	Percentage of the body that corresponds to water	Quantitative Proportion. Unit % and/or Kg. 0 a 150	Data registration form Multi-frequency Bioelectrical

				Impedance Equipment
Waist circumference	Measurement established at mid-armpit, at the point between the bottom of the last rib and the highest part of the hip.	Measurement made with a tape measure directly on the skin (without clothing). It will be measured at the height of the middle of the armpit, at the point between the bottom of the last rib and the highest part of the hip.	Unit Cm , Minimum 30 , Maximum 200	Registration form. Using tape measure
Hip circumference	specific anthropometric measurement for hip circumference measurement	Circumference of the widest part above the buttocks. Minimum 30, Maximum 200	Quantitative, Ratio Unit cm.	Recording format, measuring with tape measure.

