Blood samples will be collected in Specialized Clinical Laboratories according to NOM-253-SSA1-2012 and the laboratory sample collection manual in force in each laboratory. A venous sample will be taken to determine Complete Blood Biometry, Blood Chemistry of 27 elements, Basic thyroid profile, Glycosylated

7.8 Measuring instruments.

With all the data, a database will be built in Excel MS®. Patient satisfaction will be measured with the Likert Scale, which consists of 5 possible answers per item: very satisfied, satisfied, indifferent, dissatisfied and very dissatisfied. (attached)

7.9 Statistical analysis.

Descriptive statistical tests will be performed establishing general and group measures, determining variability measures such as standard deviation and Confidence Interval, comparative inferential tests will be performed within and between groups, for quantitative variables it is proposed as an initial T-test, which will be contrasted according to the conditions of normality and homoscedasticity of the sample. For qualitative variables, χ^2 is initially proposed, which will be contrasted according to the same conditions; one-way ANOVA and repeated measures ANOVA will also be used. Microsoft Excel 365 and SPSS V 21

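### No planned comparison measures how selectively fat is lost when the arms lose different amounts of weight, so H5 has no test and no decision rule

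*Combined protocol and SAP*

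**What the plan says.** Section 6, Assumption 4 (H5): "Tx1 will produce a selective loss of fat and preservation of muscle mass". No comparator is named and selectivity is not defined. Section 5.1 makes the difference in body composition between the two diets part of the general objective. Under Assumption 1 (H1), the Zélé method "allows a greater weight loss" than the hypocaloric diet over the same time, so the arms are expected to lose different amounts.

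Section 7.6 gives the two variables that bear on H5:

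- Fat Mass: the conceptual definition is "Percentage of body weight made up of adipose tissue", and scale and unit are "Quantitative, proportion, Unit Percentage. Minimum 9 Maximum 80". The operational definition in the same row is "Amount of fat in the body", which is an amount and not a percentage.
- Muscle Mass: "Quantitative, Ratio. Unit Kg. Minimum 10 Maximum 150", with the remark "From the point of view of body composition, it corresponds to lean mass".

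Section 7.9 says that "comparative inferential tests will be performed within and between groups", starting from a t-test for quantitative variables and adding one-way and repeated measures ANOVA. It names no derived variable, no adjustment for weight lost, and no specific test for H5.

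**The concern.** Selectivity concerns the make-up of the weight lost: of each kilogram lost, how much was fat. Fat as a percentage of current weight depends on that make-up and also on how much weight was lost. Muscle change in kg depends on both too, in the opposite direction. If the arms lost the same amount, either variable would rank the diets correctly. H1 says that they will not.

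At stake is whether the trial can answer H5 between arms at all. The two planned comparisons can point in opposite directions, and the plan gives no rule for reading them together. The choice of which one to stress would then be made after the results are known.

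**Working it through.** The documents give no figure for body composition, so there is no stated result to reproduce. All numerical inputs below are assumptions unless marked otherwise. Lean mass means all non-fat mass, in line with the table's equation of muscle with lean mass.

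**Formula.** Let f be the baseline fat fraction, l the fraction of body weight lost, and s the share of the loss that is fat. Then:

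- final fat fraction = (f − l·s) / (1 − l)
- drop in fat fraction = l·(s − f) / (1 − l)
- lean loss in kg = weight lost × (1 − s)

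The drop is a product of selectivity (s − f) and amount lost, l/(1 − l). Baseline weight cancels once the loss is a percentage of weight.

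**Illustration (90 kg, 40% fat, so 36 kg fat).**

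- Diet A loses 15% (13.5 kg), 70% of it fat. Fat lost is 9.45 kg and lean lost 4.05 kg. Fat percent becomes 26.55/76.5 = 34.7%, a drop of 5.3 points.
- Diet B loses 6% (5.4 kg), 85% of it fat. Fat lost is 4.59 kg and lean lost 0.81 kg. Fat percent becomes 31.41/84.6 = 37.1%, a drop of 2.9 points.

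B is more selective, yet fat percent ranks A first. With baseline fat from 35% to 45%, the drop is 6.2 to 4.4 points for A and 3.2 to 2.6 for B. The order is the same throughout, and also from 80 to 100 kg.

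**Amount alone drives fat percent.** At 90 kg, 40% fat and a constant 75% fat share, losing 5, 10, 15 or 20 kg lowers fat by 2.1, 4.4, 7.0 or 10.0 points.

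**How far the reversal depends on the assumptions.** At 40% fat and with B at 85%, A looks better on fat percent whenever its fat share exceeds:

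- about 56% if the losses are 15% and 6%
- about 68% if they are 15% and 10%
- about 75% if they are 10% and 8%

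The reversal can also vanish. From 90 kg and 40% fat, 15 kg at 60% fat gives 27/75 = 36.0% (drop 4.0), and 7 kg at 90% fat gives 29.7/83 = 35.8% (drop 4.2). There fat percent ranks the diets correctly.

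**Muscle in kg errs the other way.** Losing 15 kg at 85% fat costs 15 × 0.15 = 2.25 kg lean. Losing 6 kg at 75% fat costs 6 × 0.25 = 1.5 kg. Muscle kg then penalises the more selective diet.

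**Fat in kg does not repair it.** In the illustration, 9.45 kg against 4.59 kg still favours A. The fat share of the loss, 9.45/13.5 = 70% against 4.59/5.4 = 85%, gives the right order.

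**Random pairs.** Baseline fat was drawn from 35–45%, loss from 3–20% and fat share from 60–100%. The less selective diet came out ahead in 33% of pairs on fat percent, 40% on kg of fat lost and 19% on muscle kg. Fat percent and muscle kg never both favoured it, and with equal weight loss fat percent never misranked.

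**At the planned size.** A simulation assumed mean losses of 15% and 6%, mean fat shares of 72% and 82%, and SDs of 10 kg (weight), 6 points (fat), 5 points (loss) and 10 points (share). The fat percent t-test significantly favoured the less selective arm in 99% of trials at the stated 56 and 32. It did so in 96% at 36 and 21, which is what the stated 35% attrition leaves (56 × 0.65 = 36.4; 32 × 0.65 = 20.8). The muscle kg test pointed significantly the other way in essentially every trial.

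**Within one arm.** The drop is positive exactly when s > f. A within-arm fall in fat percent therefore shows that the fat share of the loss exceeded the baseline fat fraction, and no more. At 40% baseline fat, a 13.5 kg loss that is only 45% fat still lowers fat percent by 0.15 × 0.05/0.85 = 0.9 points, with 13.5 × 0.55 = 7.4 kg lean lost.

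**The case against.** The strongest reply has four parts.

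- **H5 has two limbs.** A reader might infer that H5 could be declared true, unnoticed, because the ketogenic arm simply lost more weight. The documents do not support that. H5 also requires muscle to be preserved, muscle is recorded in kg, and section 7.9 covers it. Wherever fat percent misranks, muscle kg points the other way. This stands: the likely outcome is an unresolved conflict, not a hidden false claim.
- **The units are not the cause.** A reader might also blame the pairing of percent with kg. That does not hold either, because kg of fat lost misranks too. The gap is the missing measure of selectivity.
- **H5 names no comparator.** Read within one arm, a fall in fat percent is a valid sign of disproportionate fat loss. This stands, but it sets a low bar and leaves the between-diet comparison in section 5.1 unanswered.
- **The plan is not firmly committed to percent.** The row is called Fat Mass and its operational definition is an amount; nothing ties it expressly to H5, and weight in kg allows conversion. All true. But definition, scale, unit and range agree on percent, and the total body water row shows that the table states both units where both are meant. Nothing says that fat in kg will be derived.

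**Conclusion.** The point holds as a gap in the analysis plan. When the arms lose different amounts of weight, neither fat percent nor muscle kg isolates selectivity between them; the two are biased in opposite directions, and no rule decides H5.

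That part follows from the algebra and needs only H1's prediction of unequal loss. The size does not: 5.3 against 2.9 points, and the 96–99% of simulated trials, rest on assumed losses, fat shares and SDs that the documents do not give. The ranking is stable to baseline fat of 35–45% but not to every choice of loss and fat share. The link from the Fat Mass row to H5 is inferred from the subject matter. The weight-loss hypothesis H1 is unaffected and no data are lost, so this should be settled before results are seen, but it does not threaten the trial as a whole.

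**What to change.** 1. Make the Fat Mass row in section 7.6 consistent, so that definition, operational definition and unit describe the same quantity.
2. Derive fat in kg as percent × weight at the same visit / 100, and report fat and muscle change in kg by arm.
3. State in section 7.9 that H5 is tested between arms on the fat share of weight lost, computed at arm level: mean fat kg lost divided by mean weight kg lost. Give the difference between arms with a bootstrap interval, resampling patients within arm. Name the visit, which should fall before the controls cross over (section 7.4).
4. Keep fat percent as descriptive. Lean change adjusted for weight change can be supportive, with a note that it conditions on a variable measured after randomisation.

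The arm-level ratio avoids individual ratios, which become unstable when a patient's weight change is near zero. It would itself be imprecise if an arm's mean loss were small, which is why the kg changes should stand beside it. Changing the unit to kg without step 3 would leave the problem in place.

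The cost is one derived variable, a slightly less simple test and a few lines of text. No new data are needed.

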
occurs first. And new biochemical evaluations when the decrease of Ketone Bodies below 0.4 mmol/l is detected or when patients have reached a loss of 60 to 70% of their overweight and one more when they reach their weight loss goal. Subsequently, only clinical and nutritional follow-up will be given along with psycho-emotional support and physical activity advice every 3 months up to 12 months and every 6 months up to 24 months.

7.2 Study design.

Longitudinal, Prospective, Controlled Randomized Clinical Trial.

7.3 Study population.

Patients of either sex, between 18 and 60 years of age, with a body mass index (BMI) between 30 and 35 kg/m².

7.4 Sample.

The sample will be obtained by open call through social media and all patients who come with their clinical analysis and meet the inclusion criteria will be evaluated until the sample number is reached. In order to obtain 95% power in this Controlled Clinical Trial and with a 95% CI, a 3:1 case-control ratio is established, considering a 35% attrition rate, 56 cases and 32 controls will be included and subsequently crossed to become cases. (Calculated with EPIinfo STATCALC for sample size)

Two blinded arms are proposed for the physician and the patient.

Obese patients assigned to the low-fat normoprotein controlled ketogenic diet group.

Obese patients assigned to a balanced hypocaloric diet. And who will subsequently be subjected to a controlled normoproteic low-fat ketogenic diet.

7.5 Inclusion, exclusion and elimination criteria.

7.5.1 Inclusion:

- Men and Women
- 18 to 60 years of age
- With BMI between 30 and 35 Kg/m²
- Who has not taken weight loss treatment in the last 6 months

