7.5.2 Exclusion

- Pregnant or breastfeeding patients.
- Patients with severe eating disorders, alcoholism, or drug addiction.
- Patients with severe psychological disorders (e.g. schizophrenia, bipolar disorder).
- Patients with hepatic alteration defined as increase of ALT, AST, GGT more than 4 times the reference value.
- Patients with renal impairment defined as a glomerular filtration rate below 60 ml/min.
- Patients with type 1 or insulin-dependent DM, or DM2 on insulin therapy.
- Patients with obesity caused by endocrinological diseases (except type 2 DM).
- Patients with hemopathies.
- Cancer patients.
- Patients with active cardiovascular or cerebrovascular disease (heart rhythm disorders, recent infarction [<6m], unstable angina, decompensated heart failure, recent vascular accident [<6m]).
- Patients with gout.
- Patients with renal lithiasis.
- Patients with cholelithiasis.
- Patients with depression.
- Patients with electrolyte disorders.

- Patients with orthostatic hypotension.
- Patients with an altered or abnormal electrocardiogram.

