Muscular Strength	The hand grip force measured by	Isometric muscle strength in the dominant hand	Quantitative Ratio Kg/Strength	Registration Form Digital dynamometer.
Blood Ketones	The blood ketone test measures the level of butyrate (ketones) in the blood.	Ketone bodies are substances produced by the body when cells do not receive enough glucose.	Quantitative, Ratio Unit mmol/liter Minimum 0.01 Maximum 25	Registration Form Abbott Ketone Test
Biochemical and Metabolic Variables				
Hb	Oxygen Transporting Protein in erythrocytes	Oxygen Transporting Protein in erythrocytes	Quantitative Ratio. Gr/l. minimum 10 maximum 16	Registration format. Clinical laboratory determination
Hto	Proportion of formed elements in the blood	Proportion of formed elements in the blood	Quantitative Ratio minimum 27 Maximum 50	Registration format. Clinical laboratory determination
Leukocytes	Number of white blood cells per unit volume in venous blood	Number of white blood cells per unit volume in venous blood	Quantitative, Ratio. Quantity per cc Minimum 4,000 Maximum 18,000	Registration format. Clinical laboratory determination

Neutrophils	Granular nucleated leukocytes participating in inflammatory processes.	Number of neutrophilic leukocytes	Quantitative, Ratio. Quantity per cc Minimum 4,000 Maximum 18,000	Registration format. Clinical laboratory determination
Lymphocytes	White blood cells formed by lymphatic tissue.	Number of lymphocytes in blood cell counts	Quantitative, Ratio. Quantity per cc Minimum 1,000 Maximum 8,000	Registration format. Clinical laboratory determination
Fasting Blood Glucose	Glycemia or Glycemia is the amount of glucose or sugar in the blood and is one of the sources of energy for our body, especially for the cells.	Blood sample for blood glucose with eight hours fasting time	Normoglycemia in fasting 70 to 100 mg/dl. Hyperglycemia higher than 100 mg/dl in fasting. Diabetes 126 mg/dl of fasting blood glucose.	Registration form. Blood tests
HbA1c	Measurement of glucose concentration in blood plasma level.	Glycosylated hemoglobin is considered: $HbA1c \geq 6.5\% \text{ (48 mmol/mol)}$ for diagnosis of DM2.	Categorical, Ordinal (%), 6% very low, 7% moderate, 8% high, 9% very high, 10% risk.	Registration form. Blood tests Glycosylated hemoglobin
Insulin	the amount of this hormone insulin in the blood.	Blood sample for insulin with eight hours fasting time	Hyperinsulinemia $>6\mu\text{U}/\text{ml}$	Registration form. Blood tests

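### HbA1c is typed as an ordinal variable with undefined bands, which sends it first to chi-square and, under plausible assumptions, loses much of the power to detect an HbA1c difference

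*Combined protocol and SAP*

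**What the plan says.** In the variable table of section 7.6, the scale cell for HbA1c reads "Categorical, Ordinal (%), 6% very low, 7% moderate, 8% high, 9% very high, 10% risk". The operational definition in the same row gives 6.5% or more "for diagnosis of DM2". Most other laboratory rows are typed as quantitative, on a ratio scale.

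Section 7.9 assigns tests by type of variable: "for quantitative variables it is proposed as an initial T-test", while for qualitative variables chi-square "is initially proposed, which will be contrasted according to the same conditions". One-way and repeated-measures ANOVA are also listed, without saying for which variables. Neither change from baseline nor baseline adjustment is mentioned.

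Entry requires obesity ("With BMI between 30 and 35 Kg/m²", section 7.5.1) but not diabetes. Section 7.5.2 excludes "Patients with type 1 or insulin-dependent DM, or DM2 on insulin therapy". Type 2 diabetes without insulin is allowed, and no expected share is given. Hypothesis H3 in section 6 says that weight loss on the ketogenic programme "allows the regulation of metabolic syndrome and its components", and section 5.2 lists hyperglycaemia or diabetes among the comorbidities to be followed.

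**The concern.** HbA1c is a continuous laboratory value, yet the plan's own rule would analyse it as unordered classes. Three things follow.

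- **The classes cannot be applied as written.** The row names points, not intervals, so two analysts could class the same value differently, and the choice could be made after the data are seen.
- **The scale suits the population poorly.** Four of the five labels sit at 7% or above, in a trial that does not require diabetes and excludes insulin-treated patients.
- **Information is thrown away.** With about 57 completers, a real but modest HbA1c difference could be reported as absent because of how the variable was coded.

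**Working it through.** **Plan's own figure.** There is none to reproduce for HbA1c: no distribution, expected effect, SD or power is stated. Section 7.4 gives 56 and 32 patients with 35% attrition, without naming an endpoint or effect. Completers are 56 × 0.65 = 36.4 and 32 × 0.65 = 20.8, taken as 36 and 21.

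**Step 1: the bands.** Three readings of the five points are possible: at-or-below (cuts at 6, 7, 8, 9), rounding (6.5, 7.5, 8.5, 9.5) and floor (7, 8, 9, 10). A value of 6.4% falls in the second class under the first reading and in the lowest class under the other two. Only rounding puts a boundary at 6.5%, and nothing says rounding is meant.

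**Step 2: share in the lowest band.** Assumed normal baselines, mean/SD 5.8/0.6 (A), 5.6/0.4 (B) and 6.0/0.8 (C). The share at or below 6% is Φ((6 − mean)/SD):

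- A: Φ(0.33) = 63%
- B: Φ(1.00) = 84%
- C: Φ(0) = 50%

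A second set of assumptions mixes patients without diabetes (mean 5.5–5.8, SD 0.35) and with it (mean 7.2, SD 1.0). With 0–20% diabetic, the largest band holds 60–92% (at-or-below), 83–100% (rounding) or 88–100% (floor). With 40–60% diabetic it holds 36–77%.

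**Step 3: power.** Assumed true difference 0.3 points, correlation 0.8, two-sided 5%. For the continuous analyses the non-centrality is 0.3 / (SD* × √(1/36 + 1/21)), where the root is 0.2746. SD* is:

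- change: SD × √(2 × (1 − 0.8)) = 0.632 × SD
- final value: SD
- ANCOVA: SD × √(1 − 0.8²) = 0.6 × SD

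For change in A this gives 0.3 / (0.379 × 0.2746) = 2.88, which on 55 df is 81% power. Simulation and this formula agree within about 2 points throughout.

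| Analysis | A | B | C |
|---|---|---|---|
| ANCOVA, baseline-adjusted | 84% | 99% | 61% |
| t-test on change | 81% | 98% | 58% |
| t-test on final value | 42% | 77% | 29% |
| Chi-square, final band, cuts 6/7/8/9 | 27% | 35% | 19% |
| Chi-square, rounding | 17% | 0% | 15% |
| Chi-square, floor | 1% | 0% | 12% |

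The chi-square rows are simulated without continuity correction. Repeat runs moved them by up to about 3 points (for example 18–20% for rounding in A).

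**Step 4: splitting the loss.** Going from change to final value (baseline dropped) costs 81 − 42 = 39, 98 − 77 = 21 and 58 − 29 = 29 points. Going from final value to bands at 6/7/8/9 costs 42 − 27 = 15, 77 − 35 = 42 and 29 − 19 = 10 points. Banding alone therefore removes 15/42 = 36%, 42/77 = 55% and 10/29 = 34% of what a final-value t-test would have.

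**Step 5: the mixture assumptions.** With SD of change 0.35 and a 0.3-point difference, the t-test on change has 85–88% power and chi-square on final bands 0–36%, depending on the reading. Against a final-value t-test (15–59%) the loss is sometimes small, for example 16% to 8–10%.

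**The case against.** Several objections stand and limit the point.

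- **Chi-square is only a first proposal.** Section 7.9 says it will be checked against assumptions, and it lists repeated-measures ANOVA. The row could also be read as a clinical legend. But no ordinal method is named, and the type declared in 7.6 is what decides the test.
- **The comparator matters.** Section 7.9 does not promise change or baseline adjustment even for quantitative variables. Against a t-test on final values, the loss due to banding is about a third in two of the three scenarios.
- **A reader might infer that most patients fall in one class.** The documents give no HbA1c distribution or diabetic share. In scenario C only 50% are at or below 6%, and with 40–60% diabetic no band need hold a majority.
- **A reader might infer that glycaemic effects in general are lost, because fasting glucose and insulin also look classed.** The text does not support this. Those rows state no scale type and list limits such as "Normoglycemia in fasting 70 to 100 mg/dl". Direct bilirubin, HDL and LDL also list limits and BMI lists categories, yet all four are typed quantitative. Section 7.1 requires the HOMA index, which needs numeric glucose and insulin.
- **A reader might infer that planned power is lost or that H3 fails.** HbA1c is not the endpoint of any stated power calculation. H3 does not name HbA1c as a component of metabolic syndrome, and it states no contrast between arms.
- **The number is not lost.** HbA1c is a laboratory percentage, and nothing says it will be discarded.

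**Conclusion.** The point holds for HbA1c alone. The plan types a continuous measure as ordinal, gives bands without boundaries that do not line up with its own 6.5% threshold, and routes the variable first to a test that uses neither order nor baseline. If few patients are diabetic, many or most would share one band; the documents cannot settle this.

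Under the three assumed distributions, chi-square on bands at 6/7/8/9% keeps roughly a third of the power of a t-test on change (27 of 81, 35 of 98, 19 of 58), and the other readings of the bands keep less. Part of that is the missing baseline and part is the banding. A flat statement that most power to show a glycaemic effect is lost would go too far, because it depends on unstated means, SDs, effect, cut-points and comparator, and because glucose, insulin and HOMA remain. This is a defect in a secondary measure, and it is cheap to correct.

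**What to change.** In section 7.6, retype HbA1c as quantitative, ratio scale, in %. In section 7.9, state that arms are compared on the continuous value adjusted for baseline, for example by ANCOVA. Use categories only descriptively, such as a table of baseline against follow-up class, with every boundary written out and 6.5% among them.

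For consistency, label fasting glucose and insulin quantitative as well, as the HOMA calculation already implies.

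The change is a few words in the table and one sentence in 7.9. It needs no new data, visits or patients and costs nothing. It should be made before outcome data are examined, so that neither the scale nor the cut-points can be chosen from the results.

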Arterial pH	Indicates the amount of hydrogen ions contained in the blood.	Determines the degree of acidity or alkalinity of the blood.	Quantitative, Ratio minimum 7.35 maximum 7.45	Registration form. Blood analysis
Lactic Acid	Substance produced by muscle tissue and blood cells. Lactic acid levels increase when oxygen levels decrease.	Acidic substance that accumulates in the blood and causes a decrease in pH, its ionized form is lactate.	Quantitative, Ratio 4.5 to 19 mg/l or 0.5 to 2.2 mmol/liter.	Registration form. Blood analysis
Anion Gap	Difference between anions and cations measured in the serum	Difference between anions and cations measured in serum	Quantitative, Ratio unit mEq/l minimum 8 max. 12	Registration form. Blood analysis
Excess Base	the amount of acid required to return the pH of an individual's blood to a normal value	the amount of acid required to return the pH of an individual's blood to a normal value	Quantitative, Ratio Minimum -2 maximum + 2	Registration form. Blood analysis

Satisfaction and Adherence				
Satisfaction Survey	Positive assessment of the different dimensions of the medical care received	Interrogation Very Satisfied to Very Dissatisfied	Categorical Nominal	Registration form.
Adherence to treatment	Taking medication according to the dosage of the prescribed schedule; and persistence, taking medication over time.	Interrogation Complied or did not comply with the program.	Categorical Nominal	Registration form. adherence to treatment

7.7 Data collection.

All data will be captured and recorded digitally in each of the queries through the Google Forms platform to consolidate the information in Google Sheets.

In the consultation, medical history data will be collected in the form of interrogation, weight will be determined through electronic scales, height through calibrated stadiometers, All measurements will be performed according to the WHO Physical Measurement Guide 2014 (www.who.int/surveillance/steps/Part3_Section4) Annex 1. In addition, a capillary determination of glucose and ketones will be performed at each clinical consultation. Once patients are drawn by lot they will be assigned to one of the control centers distributed in Mexico City, they will always have to go to the same control center (VIME). The consultation visits will be weekly for weight control and clinical check-up and every two weeks alternately for physical and psychological counseling.

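### The five-level satisfaction answer is ordered but typed as nominal, so the default chi-square ignores the order and usually costs power; minor, on a secondary objective

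*Combined protocol and SAP*

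**What the plan says.** Four places in the combined protocol and SAP bear on this.

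- **Section 5.2** lists patient satisfaction with the assigned program as a specific objective. Section 6 has no hypothesis about it.
- **Section 7.6**, Satisfaction Survey row: the operational definition is "Interrogation Very Satisfied to Very Dissatisfied" and the scale is "Categorical Nominal". Elsewhere in the same table HbA1c is typed as ordinal.
- **Section 7.8** describes a Likert scale with "5 possible answers per item: very satisfied, satisfied, indifferent, dissatisfied and very dissatisfied". The form is marked as attached and is not in the text.
- **Section 7.9** states that "comparative inferential tests will be performed within and between groups". For quantitative variables it starts from the t-test, "which will be contrasted according to the conditions of normality and homoscedasticity of the sample". It then says: "For qualitative variables, χ^2 is initially proposed, which will be contrasted according to the same conditions". One-way and repeated-measures ANOVA are also listed, without being assigned to any variable. No rank test, trend test or ordinal model appears.

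**The concern.** The answers run from one end of a scale to the other, so the nominal label contradicts both the row's own definition and section 7.8. Followed through, the label puts satisfaction among the qualitative variables, whose default is chi-square. Pearson's chi-square on a 2×5 table treats the five answers as interchangeable names. It spreads its sensitivity over 4 degrees of freedom, whereas the question of interest, whether one program satisfies patients more than the other, is essentially one-dimensional.

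The fallback does not lead out of this. Its conditions are normality and homoscedasticity, which do not apply to a categorical response, so they cannot direct the analyst to an ordinal method.

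At stake are some power in the satisfaction comparison and the lack of a directional effect estimate with a confidence interval. The primary comparison and the sample size are unaffected.

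**Working it through.** **Plan's own figure.** There is none for satisfaction. The overall sample of 56 cases and 32 controls (section 7.4) cannot be reproduced because no effect size, SD or rates are given. The counts are taken as they stand.

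**Inputs from the documents**
- Five ordered levels (7.8); chi-square as the default (7.9).
- 56 v 32 enrolled and 35% attrition (7.4). After attrition: 56 × 0.65 = 36.4 and 32 × 0.65 = 20.8, so 36 v 21. When the survey is given is not stated, so both sizes are shown.
- Two-sided α = 0.05, read from the 95% confidence level in 7.4; sidedness is not stated.

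**Assumptions (not in the documents)**
- Control distribution, best to worst answer: 25/35/20/12/8%.
- A proportional-odds shift in favour of the ketogenic arm, common odds ratio (OR) 2, 3 or 4.

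**Step 1: the shifted distribution.** For each cumulative control proportion c, the shifted value is OR·c/(1−c) divided by 1 + OR·c/(1−c). For OR = 3:
- control cumulative 0.25, 0.60, 0.80, 0.92; odds 0.333, 1.5, 4, 11.5
- odds × 3 = 1, 4.5, 12, 34.5; shifted cumulative 0.500, 0.818, 0.923, 0.972
- ketogenic-arm distribution 50.0/31.8/10.5/4.9/2.8%

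**Step 2: the tests.**
- Chi-square: X² = Σ(O−E)²/E on 4 df (fewer if a level is empty).
- Wilcoxon rank-sum with tie correction: z = [W − n₁(N+1)/2] / √{(n₁n₂/12)[(N+1) − Σ(t³−t)/(N(N−1))]}, where t is the number of answers at each level.

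**Step 3: simulated power** (40,000 trials per row)

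| n | OR | Chi-square | Wilcoxon | Difference (points) |
|---|---|---|---|---|
| 56 v 32 | 2 | 25.3% | 39.9% | 14.6 |
| 56 v 32 | 3 | 57.4% | 76.8% | 19.4 |
| 56 v 32 | 4 | 78.5% | 91.9% | 13.4 |
| 36 v 21 | 2 | 17.1% | 27.9% | 10.8 |
| 36 v 21 | 3 | 38.7% | 57.6% | 18.9 |
| 36 v 21 | 4 | 57.2% | 76.7% | 19.5 |

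Another run moved single figures by about one point and gave differences of 12 to 19. With three other assumed control distributions (30/35/20/10/5%, 20% at each level, 50/30/10/6/4%) and OR 2 to 4, the differences were about 12 to 20 points at 56 v 32 and 10 to 20 at 36 v 21.

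**Step 4: type I error.** At OR = 1, chi-square rejects in 4.7% (56 v 32) and 4.5% (36 v 21) of trials, and Wilcoxon in 4.9% and 5.1%. The rank test's advantage is therefore not bought with false positives.

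**Step 5: analytic cross-check.** An effect with 80% power on 1 df has noncentrality 7.85. The same noncentrality on 4 df gives 60% power. Reaching 80% on 4 df needs 11.94, and 11.94/7.85 = 1.52, so about 1.5 times the sample.

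**Step 6: when the result reverses.** Take an assumed polarised pattern: control 15/25/30/20/10%, ketogenic arm 40/10/5/10/35%. Chi-square then has 99% power at 56 v 32 and about 91% at 36 v 21, while Wilcoxon has about 4 to 5%. The loss in step 3 belongs to an ordered shift only.

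**The case against.** **The assignment to chi-square is provisional.** Section 7.9 does not mention satisfaction, and chi-square is only an initial proposal for the class of qualitative variables. This stands as a limit on wording: the test is reached through the label in 7.6. It does not remove the point, because the label is wrong and no ordinal alternative is named.

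**No confirmatory comparison is planned.** The objective is worded descriptively, section 6 has no satisfaction hypothesis, and section 7.4 names no satisfaction effect. This stands and keeps the point minor. Section 7.9 does, however, plan tests within and between groups in general.

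**The survey may have several items or a summed score.** Section 7.8 speaks of answers per item, and the form is not visible. A summed score could be quantitative and fall under the t-test. This is open, but neither possibility makes a five-level answer nominal.

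Three stronger readings are tempting and not supported:

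- *The trial would probably miss a real difference in satisfaction because of chi-square.* At OR 4, chi-square detects the difference in 57% of trials at 36 v 21, and at 56 v 32 it does so more often than not from OR 3. At OR 2 the rank test also misses about 72% of the time at 36 v 21, so small numbers explain much of the low power.
- *Sparse cells make the test invalid.* At 36 v 21 about half of the expected counts are below 5, which breaks the usual rule of thumb, but the simulated type I error stays just under 5%. No harm is shown.
- *The analysis could not show which arm is more satisfied.* The group descriptives planned in 7.9 would show the direction. What is missing is an effect estimate with an interval.

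**Conclusion.** The point holds as a minor one. The contradiction between the ordered answers (7.6 definition, 7.8) and the nominal type (7.6 scale) is in the text, and the default that follows from it ignores the order.

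The cost is about 11 to 20 points of power against a rank test, at either sample size. That figure rests on an assumed control distribution, an assumed proportional-odds shift with odds ratio 2 to 4, and, for 36 v 21, on applying the 35% attrition to the survey. Only the direction is firm, and only for an ordered shift. The missing directional estimate with a confidence interval does not depend on these assumptions.

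**What to change.** - In section 7.6, type the Satisfaction Survey as ordinal.
- In section 7.9, state that the arms are compared on each satisfaction item with the Wilcoxon rank-sum test, and that a proportional-odds ratio with its 95% CI is reported beside the distribution of answers by arm.
- State the survey time point and use responses collected before the controls cross over (section 7.4), since later control answers would reflect both programs. If items are to be summed, say so and name the analysis of the score.

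The cost is a few lines of text: no new data, no change in conduct, and SPSS is already named in 7.9. The downside is lower sensitivity to a polarised response, which the reported distribution by arm would still reveal.
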